- Obtain 2 blood samples for measurement of sUA within 48 hours prior to this visit's pegloticase infusion. Pre-infusion sUA results must be reported by the local or central laboratory prior to pegloticase infusion. If a local laboratory sample is drawn at a center other than the research site (within 48 hours prior to the pegloticase infusion), a sample for the central laboratory will be drawn prior to the pegloticase infusion on the day of the visit (see Section 9.5.1.1).
  - Stopping Rule: Subjects with an sUA level >6 mg/dL at 2 consecutive study visits beginning with the Week 2 Visit (not including post-infusion samples) will discontinue treatment and remain in the study.
- Administer MTX ≥60 minutes prior to pegloticase infusion if subject has not taken MTX within the previous 1 to 3 days.
- Document gout flares and intensity.

KRYSTEXXA IND: 010122 Protocol: HZNP-KRY-201 Version 3.0, Administrative Change 1

• Record vital signs (blood pressure [prior and post infusion], respiratory rate, temperature, and heart rate [prior and post infusion]) (see Section 9.5.4.4).

- Assess MTX compliance and re-dispense MTX.
- Ask Yes/No question regarding folic acid, gout flare prophylaxis, and IR prophylaxis compliance.
- Fill gout prophylaxis, fexofenadine, acetaminophen, and folic acid prescriptions, as needed
- Obtain a urine sample from all females of childbearing potential for performance of a pregnancy test.
- Administer IR prophylaxis (i.e., fexofenadine, acetaminophen, and methylprednisolone or hydrocortisone) (see Section 9.4.1.3).
- Administer pegloticase and record date, volume, and duration of infusion, and start/stop (inclusive of 10-mL flush) times of dosing.
- Inquire about AEs and concomitant medication use.

### 9.5.6.2.26 Week 46

- Obtain 2 blood samples for measurement of sUA within 48 hours prior to this visit's pegloticase infusion. Pre-infusion sUA results must be reported by the local or central laboratory prior to pegloticase infusion. If a local laboratory sample is drawn at a center other than the research site (within 48 hours prior to the pegloticase infusion), a sample for the central laboratory will be drawn prior to the pegloticase infusion on the day of the visit (see Section 9.5.1.1).
  - Stopping Rule: Subjects with an sUA level >6 mg/dL at 2 consecutive study visits beginning with the Week 2 Visit (not including post-infusion samples) will discontinue treatment and remain in the study.
- Administer MTX ≥60 minutes prior to pegloticase infusion if subject has not taken MTX within the previous 1 to 3 days.
- Document gout flares and intensity.
- Record vital signs (blood pressure [prior and post infusion], respiratory rate, temperature, and heart rate [prior and post infusion]) (see Section 9.5.4.4).
- Assess MTX compliance and re-dispense MTX.

KRYSTEXXA IND: 010122 Protocol: HZNP-KRY-201 Version 3.0, Administrative Change 1

 Ask Yes/No question regarding folic acid, gout flare prophylaxis, and IR prophylaxis compliance.

- Fill gout prophylaxis, fexofenadine, acetaminophen, and folic acid prescriptions, as needed.
- Obtain a urine sample from all females of childbearing potential for performance of a pregnancy test.
- Administer IR prophylaxis (i.e., fexofenadine, acetaminophen, and methylprednisolone or hydrocortisone) (see Section 9.4.1.3).
- Administer pegloticase and record date, volume, and duration of infusion, and start/stop (inclusive of 10-mL flush) times of dosing.
- Inquire about AEs and concomitant medication use.

### 9.5.6.2.27 Week 48

- Obtain 2 blood samples for measurement of sUA within 48 hours prior to this visit's pegloticase infusion. Pre-infusion sUA results must be reported by the local or central laboratory prior to pegloticase infusion. If a local laboratory sample is drawn at a center other than the research site (within 48 hours prior to the pegloticase infusion), a sample for the central laboratory will be drawn prior to the pegloticase infusion on the day of the visit (see Section 9.5.1.1).
  - Stopping Rule: Subjects with an sUA level >6 mg/dL at 2 consecutive study visits beginning with the Week 2 Visit (not including post-infusion samples) will discontinue treatment and remain in the study.
- Administer MTX ≥60 minutes prior to pegloticase infusion if subject has not taken MTX within the previous 1 to 3 days.
- Document gout flares and intensity.
- Record vital signs (blood pressure [prior and post infusion], respiratory rate, temperature, and heart rate [prior and post infusion]) (see Section 9.5.4.4).
- Assess MTX compliance and re-dispense MTX.
- Ask Yes/No question regarding folic acid, gout flare prophylaxis, and IR prophylaxis compliance.
- Fill gout prophylaxis, fexofenadine, acetaminophen, and folic acid prescriptions, as needed.

KRYSTEXXA IND: 010122

• Obtain a urine sample from all females of childbearing potential for performance of a pregnancy test.

- Administer IR prophylaxis (i.e., fexofenadine, acetaminophen, and methylprednisolone or hydrocortisone) (see Section 9.4.1.3).
- Administer pegloticase and record date, volume, and duration of infusion, and start/stop (inclusive of 10-mL flush) times of dosing.
- Obtain a blood sample (1 sample) for measurement of sUA after the end of pegloticase infusion prior to discharge.
- Inquire about AEs and concomitant medication use.

#### 9.5.6.2.28 Week 50

- Obtain 2 blood samples for measurement of sUA within 48 hours prior to this visit's pegloticase infusion. Pre-infusion sUA results must be reported by the local or central laboratory prior to pegloticase infusion. If a local laboratory sample is drawn at a center other than the research site (within 48 hours prior to the pegloticase infusion), a sample for the central laboratory will be drawn prior to the pegloticase infusion on the day of the visit (see Section 9.5.1.1).
  - Stopping Rule: Subjects with an sUA level >6 mg/dL at 2 consecutive study visits beginning with the Week 2 Visit (not including post-infusion samples) will discontinue treatment and remain in the study.
- Administer MTX ≥60 minutes prior to pegloticase infusion if subject has not taken MTX within the previous 1 to 3 days.
- Document gout flares and intensity.
- Record vital signs (blood pressure, one measurement [prior and post infusion], respiratory rate, temperature, and heart rate [prior and post infusion]) (see Section 9.5.4.4).
- Assess MTX compliance and dispense.
- Ask Yes/No question regarding folic acid, gout flare prophylaxis, and IR prophylaxis compliance.
- Obtain a urine sample from all females of childbearing potential for performance of a pregnancy test.
- Administer IR prophylaxis (i.e., fexofenadine, acetaminophen, and methylprednisolone or hydrocortisone) (see Section 9.4.1.3Error! Reference source not found.).

Horizon Therapeutics Ireland DAC Date: 01 April 2020

Protocol: HZNP-KRY-201 Version 3.0, Administrative Change 1

KRYSTEXXA IND: 010122

• Administer pegloticase and record date, volume, and duration of infusion, and start/stop (inclusive of 10-mL flush) times of dosing.

- Obtain a blood sample (1 sample) for measurement of sUA after the end of pegloticase infusion prior to discharge.
- Inquire about AEs and concomitant medication use.

Note: MTX will be taken one week following the Week 50 Visit and Folic Acid will be taken until just prior to the Week 52 Visit.

# 9.5.6.3 End of Pegloticase Infusions Visit

Subjects who end pegloticase infusions prior to Week 52 will complete the End of Pegloticase Infusions Visit procedures following their final infusion. Subjects should continue to participate in all visits through the end of the study. Subjects must complete selected study visits at the study site during key efficacy and safety collections Weeks 10, 12, 14, 20, 22, 24, 32, 34, 36, 48, 50 and 52, so that sUA labs and other key assessments can be completed. Visits between these key efficacy and safety collection visits, for subjects who have stopped infusions, may be completed in person or via a telephone visit option to collect AEs, concomitant medication and gout flare information (See 9.3.3.1.1).

The following procedures will be completed at the End of Pegloticase Visit:

- Investigator Assessment of Clinical Status.
- Document gout flares and intensity.
- Perform a targeted physical examination should include heart, lungs and abdominal exam and joint and skin evaluation and assessment of AEs. Any finding will be recorded as an AE.
- Record vital signs (blood pressure, respiratory rate, temperature, and heart rate including the measurement of weight. (see Section 9.5.4.4).
- Collect swollen/tender joint counts; administer HAQ; and record patient and physician global assessments and joint pain assessment responses.
- Assessment of Tophi.
- Assess MTX compliance.
- Ask Yes/No question regarding folic acid, gout flare prophylaxis, and IR prophylaxis compliance.

Horizon Therapeutics Ireland DAC Date: 01 April 2020

Protocol: HZNP-KRY-201 Version 3.0, Administrative Change 1

KRYSTEXXA IND: 010122

 Obtain a urine sample from all females of childbearing potential for performance of a pregnancy test.

- Obtain blood samples for hematology and clinical chemistry analysis.
- Obtain a urine sample for uric acid:creatinine ratio.
- Obtain blood samples for pegloticase PK analysis.
- Obtain blood samples for anti-PEG and anti-uricase IgG antibodies.
- Obtain a blood sample (1 sample) for measurement of sUA.
- Inquire about AEs and concomitant medication use.
- Perform DECT (if applicable). DECT may be completed within +/- 5 days of the scheduled visit. Subjects who end pegloticase infusions prior to Week 52 should follow the scheduled timepoints but avoid a repeat DECT scan within 6 weeks of a prior scan.

# 9.5.6.4 Week 52/End of Study/Early Termination Visit

- Investigator Assessment of Clinical Status.
- Perform a targeted physical examination should include heart, lungs and abdominal exam and joint and skin evaluation and assessment of AEs. Any finding will be recorded as an AE.
- Assessment of Tophi.
- Document gout flares and intensity.
- Record vital signs (blood pressure, respiratory rate, temperature, heart rate include measurement of weight. (see Section 9.5.4.4).
- Collect swollen/tender joint counts; administer HAQ; and record patient and physician global assessments and joint pain assessment responses.
- Assess MTX compliance.
- Ask Yes/No question regarding folic acid, gout flare prophylaxis, and IR prophylaxis compliance.
- Obtain a sample from all females of childbearing potential for performance of a pregnancy test.
- Obtain blood samples for hematology and clinical chemistry analysis.

KRYSTEXXA IND: 010122

- Obtain a urine sample for uric acid:creatinine ratio.
- Obtain a blood sample (1 sample) for measurement of sUA.
- Obtain blood samples for pegloticase PK analysis.
- Obtain blood samples for anti-PEG and anti-uricase IgG antibodies.
- Inquire about AEs and concomitant medication use.
- Perform DECT (if applicable). DECT may be completed within +/- 5 days of the scheduled visit.

#### 9.5.6.5 Safety Follow-up Phone/Email/Site Visits

Thirty (30) days after the last MTX dose, subjects will be contacted by telephone or email or may visit the site to review SAEs. Subjects who are females of childbearing potential will be asked to confirm that ovulation has occurred. If the subject has not ovulated, the subject will be requested to return to the site for a urine pregnancy test.

#### 9.5.6.6 MTX Partner Pregnancy Follow-up

Subjects who are non-vasectomized males, a phone/e-mail/site visit inquiry will be conducted 3 months after MTX discontinuation regarding partner pregnancy (this can be conducted at the 3 month Post Treatment Follow-up Visit).

# 9.5.6.7 Post Treatment Follow-up

The intent is for at least 6 months of follow-up on each subject after cessation of pegloticase infusions. If these 6 months occur prior to end of study at Week 52, such as in the case of a subject who ends pegloticase infusions on or before Week 24, there will be no follow-up visits after the Week 52/End of Study Visit. For subjects who end pegloticase infusions between Weeks 26 and 36, there will be at least 3 months of follow-up while the subject remains on-study prior to Week 52, and then one follow-up visit after the Week 52/End of Study Visit. For subjects who end pegloticase infusions between Weeks 38 and 52, there will be two follow-up visits at intervals of 3 months apart after the Week 52/End of Study Visit. The following procedures will be completed at the 3 and 6 month Post Treatment Follow-up Visits:

- Document gout flares and intensity.
- Record vital signs (blood pressure, respiratory rate, temperature, heart rate and weight). (see Section 9.5.4.4).
- Perform a targeted physical examination should include heart, lungs and abdominal exam and joint and skin evaluation and assessment of AEs. Any finding will be recorded as an AE.

KRYSTEXXA IND: 010122

• Collect swollen/tender joint counts; administer HAQ; and record patient and physician global assessments and joint pain assessment responses.

- Assessment of Tophi.
- Obtain blood samples for hematology and clinical chemistry analysis.
- Obtain a blood sample (1 sample) for measurement of sUA.
- Obtain blood samples for anti-PEG and anti-uricase IgG antibodies prior to the infusion (3 Month Post Treatment Follow-up Visit only).
- Inquire about AEs and concomitant medication use.

#### 9.6 Statistical Methods and Determination of Sample Size

Detailed statistical analyses will be presented in a separate statistical analysis plan (SAP). Some key points identified for statistical analyses are outlined below.

# 9.6.1 Endpoints

# 9.6.1.1 Primary Endpoint

The primary efficacy endpoint is the proportion of Month 6 (Weeks 20, 22, and 24) responders, defined as subjects achieving and maintaining sUA <6 mg/dL for at least 80% of the time during Month 6.

#### 9.6.1.2 Secondary Endpoints

The secondary efficacy endpoints are:

- The proportion of Month 3 (Weeks 10, 12, and 14) responders, defined as subjects achieving and maintaining sUA <6 mg/dL for at least 80% of the time during Month 3.
- The proportion of overall responders, defined as subjects achieving and maintaining sUA <6 mg/dL for at least 80% of the time during Month 3 (Weeks 10, 12 and 14) and Month 6 (Weeks 20, 22 and 24) combined.
- The proportion of 5 mg/dL responders during Month 3, during Month 6, and overall (Months 3 and 6 combined), defined as subjects achieving and maintaining sUA < 5 mg/dL for at least 80% of the time during each timepoint.
- The mean change from baseline to Weeks 14, 24, 36, and 52 in sUA.

#### 9.6.1.3 Exploratory Endpoints

The exploratory efficacy endpoints are:

• The proportion of Month 9 (Weeks 32, 34 and 36) responders, defined as subjects achieving and maintaining sUA <6 mg/dL for at least 80% of the time during Month 9.

- The proportion of Month 12 (Weeks 48, 50 and 52) responders, defined as subjects achieving and maintaining sUA <6 mg/dL for at least 80% of the time during Month 12.
- The proportion of Month 9 (Weeks 32, 34 and 36) 5 mg/dL responders, defined as subjects achieving and maintaining sUA <5 mg/dL for at least 80% of the time during Month 9.
- The proportion of Month 12 (Weeks 48, 50 and 52) 5 mg/dL responders, defined as subjects achieving and maintaining sUA <5 mg/dL for at least 80% of the time during Month 12.
- The time to first sUA > 6 mg/dL.
- The time to two consecutive sUAs > 6 mg/dL (stopping rule).
- The mean change from baseline to Weeks 24, 36, and 52 in urate volume and bone erosions due to gout using DECT.
- The mean change from baseline in number of joints affected by tophi
- The mean change from baseline to Weeks 14, 24, 36, and 52 in tender joint count (68 point scale).
- The mean change from baseline to Weeks 14, 24, 36, and 52 in swollen joint count (66 point scale).
- The mean change from baseline to Weeks 14, 24, 36, and 52 in HAQ-DI.
- The mean change from baseline to Weeks 14, 24, 36, and 52 in HAQ pain score.
- The mean change from baseline to Weeks 14, 24, 36, and 52 in HAQ health score.
- The mean change from baseline to Weeks 14, 24, 36, and 52 in patient global assessment of gout.
- The mean change from baseline to Weeks 14, 24, 36, and 52 in physician global assessment of gout.
- The mean change from baseline to Weeks 14, 24, 36, and 52 in subject assessment of average, least, and worst joint pain.
- The proportion of subjects achieving 20%, 50%, or 70% improvement based on gout chronic response criteria at Weeks 14, 24, 36, and 52.

#### 9.6.1.4 Pharmacokinetic and Anti-drug Antibody Endpoints

The PK and anti-drug antibody endpoints are:

- PK of pegloticase in subjects receiving concomitant MTX.
- Incidence of anti-PEG and anti-Uricase IgG antibodies.

# 9.6.1.5 Safety and Tolerability Endpoints

Safety and tolerability endpoints are:

• Incidence of IRs, anaphylaxis, gout flares, cardiovascular events, and the AE/SAE profile overall, and potentially attributed to the combination of pegloticase and MTX.

# 9.6.2 Populations for Analysis

The following analysis populations will be defined for this study:

- Intent-to-treat (ITT) population: all subjects who take at least one dose of MTX
- Modified intention-to-treat (mITT) population: all subjects who receive at least 1 dose of pegloticase
- Pharmacokinetic (PK) population: all subjects who receive at least 1 dose of pegloticase and have a post-pegloticase sample evaluable for PK analysis

# 9.6.3 Demographic Variables

Demographic data, including age, race, and gender, medical history, and other disease characteristics, will be summarized using descriptive statistics. Summaries of demographic variables will be provided for the ITT and mITT populations. Listings will include all screened subjects.

### 9.6.4 Subject Disposition

The number and percentage of subjects who completed the study and who discontinued the study prematurely along with the reasons for discontinuation will be summarized for each analysis population.

#### 9.6.5 Efficacy Endpoint Analysis

Efficacy analyses will be performed using the mITT and ITT populations. There will be no statistical testing. Continuous variables will be summarized using descriptive statistics (number of subjects, mean, median, standard deviation, minimum, and maximum). Categorical variables will be summarized using frequencies and percentages. Unless otherwise specified, baseline is defined as the last non-missing observation prior to the first dose of MTX. Additional details will be provided in the SAP.

#### 9.6.5.1 Primary and Secondary Endpoint Analysis

The primary efficacy endpoint is the proportion of responders during Month 6. A responder is defined as a subject for whom the proportion of time that the sUA-time curve is <6 mg/dL during Month 6 (Weeks 20, 22, and 24) is at least 80%. The proportion of time that the sUA level is below 6 mg/dL is defined as the ratio of the time during which the sUA level remains below 6 mg/dL (using linear interpolation, if necessary) to the entire time interval during Month 6. The proportion of responders will be summarized, along with a 95% exact (Clopper-Pearson) confidence interval for the proportion. The proportion of Month 3, overall (Months 3 and Month 6 combined), and 5 mg/dL responders (during Month 3, Month 6, and overall) will be summarized similarly.

Protocol: HZNP-KRY-201

KRYSTEXXA IND: 010122

Version 3.0, Administrative Change 1

A subject will be declared a non-responder if the subject had sUA level > 6 mg/dL at 2 consecutive study visits beginning with the Week 2 Visit. In addition, a subject who withdraws from the study for any reason (other than stopping rule) after the first dose of pegloticase in the pegloticase + IMM Period and prior to or during Month 6 (for the primary endpoint) or Months 3 or 6 (for the secondary endpoints) will be considered a non-responder if sUA values are not collected at planned timepoints.

sUA will be summarized at each visit and change from baseline to each visit with descriptive statistics.

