#### Statistical Analysis on Efficacy Parameters

The efficacy analysis will be performed using the modified intention-to-treat (mITT) population, defined as all enrolled subjects who received ≥1 dose of pegloticase. The proportion of Month 6 responders will be summarized, along with a 95% confidence interval for the proportion. The proportion of Month 3 and overall (Months 3 and 6 combined) responders will be analyzed similarly.

A subject will be declared a non-responder if the subject had sUA level > 6 mg/dL at 2 consecutive study visits beginning with the Week 2 Visit. In addition, a subject who withdraws from study treatment for any reason after the first dose of pegloticase in the Pegloticase + IMM Period and prior to Month 6 (for the primary endpoint) or Month 3 (for the secondary endpoint) will be considered a non-responder if sUA values are not collected at the planned time points.

Swollen/tender joint counts, HAQ scores, patient and physician global assessment scores, subject assessment of joint pain scores, and mean sUA changes from baseline and values at baseline and each visit will be summarized with descriptive statistics. The proportion of subjects achieving 20%, 50%, or 70% improvement based on gout chronic response criteria will be summarized. For subjects with DECT scans, changes from baseline and values at Weeks 24, 36 and 52 for urate volume will be summarized with descriptive statistics.

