#### 9.5.1.1 Serum Uric Acid

Serum samples for measurement of sUA levels will be collected at the Screening Visit (within 2 weeks prior to the first dose of MTX at Week -4), the Week -4 Visit (prior to the first dose of MTX), and the Week -2 Visit during the MTX Run-in Period; within 48 hours prior to each pegloticase infusion (except on Day 1 when only 1 pre-infusion sample is required) and after the end of each pegloticase infusion prior to discharge, from the Pegloticase + IMM Period through PRIVATE AND CONFIDENTIAL INFORMATION OF HORIZON THERAPEUTICS IRELAND DAC Page 62 of 129

KRYSTEXXA IND: 010122 Protocol: HZNP-KRY-201 Version 3.0, Adminstrative Change 1

week 24 and at Weeks 32, 34, 36, 48 and 50; within 48 hours prior to each pegloticase infusion at Weeks 26, 28, 30, 38, 40, 42, 44 and 46 during the Pegloticase + IMM Period; and at the at the End of Pegloticase Infusions Visit (if applicable); at the Week 52/End of study/Early Termination Visit and Month 3 and Month 6 Visits. (Section 2.1) Optional (subjects who agree to participate) visits for frequent sampling for additional non-infusion visit sUA sampling (random, morning preferred) will occur at Week 1 and Week 7.

Two separate samples/tubes of blood will be collected within 48 hours prior to the pegloticase infusion for assessment of sUA (except on Dayl when only 1 pre-infusion sample is required for the central laboratory). One sample/tube will be assessed by the site's local laboratory to be used for on-study subject management; pre-infusion sUA results must be reported by the local or central laboratory prior to each pegloticase infusion. If a local laboratory sample is drawn (within 48 hours prior to the pegloticase infusion), a sample for the central laboratory will be drawn prior to the pegloticase infusion on the day of the visit. The second sample/tube will be sent to the central laboratory for analysis and recording in the database. Each sample/tube will be labelled with the date and time of the sample collection. The date and time of blood sample collection will be recorded. See the Laboratory Manual for instructions for alternate scenarios.

A subject with sUA level >6 mg/dL (based on the local or central laboratory) at 2 consecutive study visits, beginning with the Week 2 Visit, will be discontinued from pegloticase treatment and remain on study.

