- Stopping Rule: Subjects with an sUA level >6 mg/dL at 2 consecutive study visits beginning with the Week 2 Visit (not including post-infusion samples) will discontinue treatment and remain in the study.
- Administer MTX \ge 60 minutes prior to pegloticase infusion if subject has not taken MTX within the previous 1 to 3 days.
- Document gout flares and intensity.
- Record vital signs (blood pressure [prior and post infusion], respiratory rate, temperature, and heart rate [prior and post infusion]) (see Section 9.5.4.4).
- Assess MTX compliance and re-dispense MTX.
- Ask Yes/No question regarding folic acid, gout flare prophylaxis, and IR prophylaxis compliance.
- Fill gout prophylaxis, fexofenadine, acetaminophen, and folic acid prescriptions, as needed.
- Obtain a urine sample from all females of childbearing potential for performance of a pregnancy test.
- Administer IR prophylaxis (i.e., fexofenadine, acetaminophen, and methylprednisolone or hydrocortisone) (see Section 9.4.1.3).
- Administer pegloticase and record date, volume, and duration of infusion, and start/stop (inclusive of 10-mL flush) times of dosing.
- Inquire about AEs and concomitant medication use.

## 9.5.6.2.17 Week 28

• Obtain 2 blood samples for measurement of sUA within 48 hours prior to this visit's pegloticase infusion. Pre-infusion sUA results must be reported by the local or central laboratory prior to pegloticase infusion. If a local laboratory sample is drawn at a center other than the research site (within 48 hours prior to the pegloticase infusion), a sample

for the central laboratory will be drawn prior to the pegloticase infusion on the day of the visit (see Section 9.5.1.1).

- Stopping Rule: Subjects with an sUA level >6 mg/dL at 2 consecutive study visits beginning with the Week 2 Visit (not including post-infusion samples) will discontinue treatment and remain in the study.
- Administer MTX ≥60 minutes prior to pegloticase infusion if subject has not taken MTX within the previous 1 to 3 days.
- Document gout flares and intensity.
- Record vital signs (blood pressure [prior and post infusion], respiratory rate, temperature, and heart rate [prior and post infusion]) (see Section 9.5.4.4).
- Assess MTX compliance and re-dispense MTX.
- Ask Yes/No question regarding folic acid, gout flare prophylaxis, and IR prophylaxis compliance.
- Fill gout prophylaxis, fexofenadine, acetaminophen, and folic acid prescriptions, as needed.

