#### 9.6.8 Interim Analyses

No formal interim analysis is planned for this study. Efficacy and safety data may be summarized after all subjects enrolled in the study have completed the Week 14 visit or discontinued, and after all subjects have completed Week 24 or discontinued. Additional summary of the data may be performed periodically throughout the study, and safety data will be summarized regularly for safety monitoring. Final analysis will occur when all subjects have completed the study.

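### The two-visit non-responder rule names no last visit, so read literally it lets sUA values after Week 14 or Week 24 overturn a Month 3, Month 6 or overall response

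*Protocol*

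**What the plan says.** Section 9.6.1.1 defines the primary endpoint within one month: responders are "defined as subjects achieving and maintaining sUA <6 mg/dL for at least 80% of the time during Month 6", that is, over Weeks 20, 22 and 24. Section 9.6.5.1 makes this operational as the share of Month 6 during which the interpolated sUA curve is below 6 mg/dL. Month 3 (Weeks 10, 12 and 14) and overall response (both months combined) are handled in the same way.

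Section 9.6.5.1 then adds an override. A subject is "declared a non-responder if the subject had sUA level > 6 mg/dL at 2 consecutive study visits beginning with the Week 2 Visit". The synopsis, under Statistical Analysis on Efficacy Parameters, has the same rule. Neither place gives a last visit or names an endpoint.

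The next sentence in each place, on withdrawals, does name the month. The synopsis has "prior to Month 6 (for the primary endpoint) or Month 3 (for the secondary endpoint" and 9.6.5.1 has "prior to or during Month 6 (for the primary endpoint) or Months 3 or 6 (for the secondary endpoints".

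Two other places attach the non-responder label to the same two-visit criterion, again with no end: Section 7.1.2 and the sUA footnote (footnote 20) to the Schedule of Assessments in 2.1.

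**The concern.** The criterion stays live long after Month 6. The visit instructions repeat it at Weeks 26, 28 and 50, among others: "Stopping Rule: Subjects with an sUA level >6 mg/dL at 2 consecutive study visits beginning with the Week 2 Visit". Section 9.5.1.1 also calls for sUA "at the Week 52/End of study/Early Termination Visit and Month 3 and Month 6 Visits".

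Data from outside a scoring window could therefore cancel a response that the endpoint's own definition grants. The override can only turn responders into non-responders, so any bias is downward. It would affect the estimated rate and its confidence interval, and with 12 to 16 subjects a single change is visible.

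Classification could also depend on when the data are cut. Section 9.6.8 says "Efficacy and safety data may be summarized after all subjects enrolled in the study have completed the Week 14 visit or discontinued", and it allows another summary after Week 24. A subject counted as a Month 6 responder in that summary could be a non-responder in the final analysis with no change to any Month 6 value.

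**Working it through.** **1. Two rules applied to one subject (illustrative values).** Take sUA = 3 mg/dL at Weeks 18, 20, 22 and 24, and 7 mg/dL at Weeks 26 and 28. Month 6 is taken to run from Week 20 to Week 24.

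- Endpoint definition (9.6.1.1, 9.6.5.1): the interpolated curve is 3 mg/dL for 4 of 4 weeks. 4/4 = 100%, which is at least 80%, so the subject is a responder.
- Override (9.6.5.1): Weeks 26 and 28 are two consecutive study visits after Week 2 with sUA above 6 mg/dL, so the subject is a non-responder.

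For Month 3, a pair at Weeks 16 and 18 is enough to produce the same conflict. Values at Weeks 16 to 24 properly bear on Month 6 and overall response but not on Month 3, so one common end visit would not serve all endpoints.

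**2. How long the literal rule stays open.** Two-weekly visits after Week 24 run from Week 26 to Week 52: (52 − 26)/2 + 1 = 14 visits. After Week 14 they run from Week 16: (52 − 16)/2 + 1 = 19 visits. sUA is also drawn at the 3 and 6 month post-treatment visits (9.5.6.7), which the literal wording does not exclude.

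**3. The plan's own figure.** Section 9.6.9 says 10/13 responders gives a 95% lower limit of about 46%. The Clopper-Pearson limits are the 0.025 quantile of Beta(x, n − x + 1) and the 0.975 quantile of Beta(x + 1, n − x). With x = 10 and n = 13 they are 46.2% and 95.0%, so the figure reproduces.

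**4. Size per reclassified subject.** The change is 100/n points.

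| n | points per subject |
|---|---|
| 12 | 8.3 |
| 13 | 7.7 |
| 14 | 7.1 |
| 15 | 6.7 |
| 16 | 6.3 |

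Applied to the plan's example:

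| Month 6 responders overturned | Rate | 95% Clopper-Pearson |
|---|---|---|
| 0 | 10/13 = 76.9% | 46.2% to 95.0% |
| 1 | 9/13 = 69.2% | 38.6% to 90.9% |
| 2 | 8/13 = 61.5% | 31.6% to 86.1% |

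These rows illustrate the effect and are not expected values. The protocol gives no rate at which Month 6 responders later lose response.

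**The case against.** The best answer is that nobody would apply the rule in its open-ended form, and the context supports this. Each responder endpoint is defined within its own month. Section 9.6.5.2 scores Months 9 and 12 in a similar manner to the earlier months. If the rule had no end, a late loss would cancel response at every earlier month, and separate monthly rates would lose most of their purpose. Later loss already has its own endpoint in 9.6.1.3: "The time to two consecutive sUAs > 6 mg/dL (stopping rule"). Summaries after Weeks 14 and 24 make sense only if response is settled by then. Section 9.6 also leaves detail to the SAP, which is not at hand and may state the cut-off.

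This stands as to intent, and it limits the severity. It does not remove the point. The protocol does not defer this rule. It states it, for the primary endpoint, in a form that can conflict with that endpoint's definition, beside a withdrawal sentence that is bounded. An SAP that copied the wording would carry the conflict forward.

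A reader might also infer that one late loss would cost the trial its comparison with 43.5%, since the lower limit falls from 46.2% to 38.6% between 10/13 and 9/13. The documents do not support that as a consequence. Although 9.6.9 frames the sample size around an exact test against 43.5%, 9.6.5 rules out statistical testing and the primary objective is to estimate a rate. Moreover, 10/13 is the smallest count at n = 13 whose lower limit exceeds 43.5%, so one fewer falls below it by construction.

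**Conclusion.** The point holds as a defect of wording in a stated scoring rule. The override has a start and no end, and followed literally it can classify a subject with 100% of Month 6 below 6 mg/dL as a non-responder. No section of the protocol supplies the missing bound.

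The possible effect is a downward bias of 100/n points per reclassified subject, or 6.3 to 8.3 points over the planned 12 to 16 subjects. It arises only if the rule is applied literally and at least one responder later has two consecutive values above 6 mg/dL. Otherwise it is zero. A reader might infer that bias is likely, or that an open-ended rule was meant. The protocol gives no late-loss rate to support the first, and its structure points against the second. This is a minor to moderate correction.

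**What to change.** For scoring only:

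- In 9.6.5.1 and the synopsis, state that for each responder endpoint the override counts only pairs of consecutive study visits from Week 2 up to and including the last visit of that endpoint's window. That is Week 14 for Month 3, and Week 24 for Month 6 and overall. If the rule is applied to Months 9 and 12, it is Week 36 and Week 52. The 5 mg/dL versions follow the same windows. A pair completed after the window does not count.
- In 7.1.2 and footnote 20 of 2.1, make the non-responder label refer to that scoring rule. Editing only 9.6.5.1 and the synopsis would leave open-ended wording elsewhere.
- As a separate clarification, say that the override uses pre-infusion samples, as the Individual Subject Stopping Rule in the synopsis already does. This concerns the override and not the sUA-time curve.

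The clinical stopping rule stays unchanged. Later loss remains captured by the Month 9, Month 12 and time-to-event endpoints. The cost is a clause in two places, matching wording in two more and one clarifying sentence, with no new data and no change to subject management.
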